Quantitative Electroencephalogram (QEEG) Predictors of Response to Psychotherapy
Versus Antidepressant Treatment in Depression

Identifiers: NCT00824044

Unique Protocol ID: 2008-P-000838

Date prepared: 12/7/2017

Summary:

A-priori expectation from prior **medication** work is a decrease in theta activity from baseline at week 1 in responders, and an increase in non-responders. Prior work showed an increase in theta activity in **placebo** responders (and little change in non-responders). (See attached manuscript that describes changes in theta Cordance over time in both placebo and medication groups. See Fig 4 on page 128.) Also, ATR is expected to be higher in medication responders than non-responders after 1 week on antidepressant.

Methods:

ATR and Power metrics were calculated from available EEGs at baseline and subsequent visits. Change in Power between baseline and subsequent visits were derived. The data were analyzed for 3 groups: Pooled, Drug-only, Drug+CBT.

In a completer analysis (not an intent to treat), independent sample t tests were used to assess the relationship between responders (greater than or equal to 50 % reduction in the primary outcome (HAMD-17 score)) and change in QEEG metrics across time.

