### C. *QEEG:*

Quantitative electroencephalography (QEEG) has emerged in recent years as a technology that may help predict eventual response to antidepressants as early as the first week of prescription and may help shed light on the mechanism(s) of action of depression treatments. QEEG has enabled spectral analysis of EEG signals using a digitized signal on magnetic or optical media, providing information that cannot be extracted through visual inspection of the traditional EEG paper tracings. Cordance, a QEEG measure integrating absolute and relative power of the signal, was shown to be decreased in subjects with MDD, compared to normal

subjects (Cook et al, 1998). Researchers have reported differences between responders and non-responders to antidepressant treatment with respect to the absolute or relative power of the EEG signal (Ulrich et al., 1994; Knott et al, 1996). Subsequently, QEEG has been shown to have utility in predicting clinical response to SSRI antidepressants (Cook et al, 1999). Specifically, in a case series, Cook and Leuchter (2001) found that clinical response to antidepressant medications was preceded by decreases in QEEG measurements (theta cordance) in the prefrontal brain regions.

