## **II. Specific Aims:**

Primary Aim 1: To determine whether QEEG technology can predict whether a patient with MDD will respond to CBT.

Hypothesis 1: Clinical response (defined as >50% change in HAMD-17 from beginning to endpoint) will correlate with changes in QEEG metrics (ATR, EEG Bispectrum, cordance estimates) from beginning to two weeks after starting treatment.

Primary Aim 2: To determine whether there are unique biological changes in patients undergoing CBT, as measured by the QEEG, that are different than those associated with antidepressants (SSRIs).

Hypothesis 2: QEEG parameters, different from those that predict response to pharmacotherapy, will be associated with response to CBT.

Secondary Aim 1: To determine whether there are correlations between QEEG patterns and changes in clinical functioning, assessed by clinical and self-rated instruments (SF-36, Symptom Questionnaire, Beck Depression Inventory), in both arms (CBT vs. escitalopram).

Secondary Aim 2: To determine whether there are any correlations between QEEG metrics and clinical variables (gender, age, comorbid anxiety, chronicity of depression).

Secondary Aim 3: To determine whether the behavioral processes associated with reward responsiveness in a depressed population change as a function of treatment.

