## V. Study Procedures

### a) *Study visits and parameters to be measured:*

The study involves the enrollment of 30 outpatients with major depressive disorder.

Patients screened for the study and found to be eligible will return for their baseline visit after one week, at which eligible patients (n = 30) will be randomized to either CBT or to standard pharmacotherapy with an SSRI (escitalopram 10-20mg) for 12 weeks.

The CBT group will receive twelve weekly 50-minute individual sessions over the course of 12 weeks conducted by experienced therapists who are trained in manual based CBT. The medication group will receive open label treatment of escitalopram, 10-20 mg/day, flexible dose, for 12 weeks, and will be seen every two weeks by a study physician. In both arms, study assessors, who are blind to treatment condition, will assess patients monthly (week 0, 4, 8, and 12), and are responsible for the primary outcome measure (HAMD-17).

The QEEG will be administered 5 times during the study (week 0, 1, 2, 8 and endpoint) allowing us to assess whether there are any correlations between QEEG patterns and changes in clinical functioning. We will record EEG from a fronto-parieto-temporal derivation using a 4-channel EEG Monitor (Aspect Medical Systems) connected to the subject via disposable EEG electrodes. The adhesive material of the electrodes is similar to that found in ECG electrodes. All recordings will be analyzed off-line to generate QEEG metrics. Once such QEEG metric, the ATR, is a complex index derived from left-right asymmetry of combined theta+alpha (4-12Hz) power, relative theta power, and percent change from baseline in relative theta power, and ranges from 0 (low probability of response) to 100 (high probability of response). De-identified data will be shared with Aspect Medical Systems for offline calculation of EEG-based metrics.

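### The SAP does not test Hypothesis 1 as stated: Bispectrum is omitted, cordance is undetermined, and neither the week-2 change nor a CBT-only group is designated

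*SAP*

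**What the plan says.** **Protocol, II. Specific Aims.** Primary Aim 1 asks whether QEEG predicts response to CBT. Hypothesis 1, which serves that aim, says that clinical response "will correlate with changes in QEEG metrics (ATR, EEG Bispectrum, cordance estimates) from beginning to two weeks after starting treatment". That fixes three metrics and one window.

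**Protocol, V. Study Procedures, a).** "The QEEG will be administered 5 times during the study (week 0, 1, 2, 8 and endpoint"), so there are four post-baseline recordings, and week 2 is one of them.

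**Protocol, VI. Statistical Analysis, a).** A Mann-Whitney test compares QEEG changes between CBT responders and non-responders, and a logistic regression uses other EEG measures as predictors. Neither is tied to a named metric or week.

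**SAP, Methods.** "ATR and Power metrics were calculated from available EEGs at baseline and subsequent visits". "Change in Power between baseline and subsequent visits were derived". Completer t tests then relate responder status to "change in QEEG metrics across time". The groups analysed are Pooled, Drug-only and Drug+CBT.

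**SAP, Summary.** Cordance appears only in a reference to an attached manuscript that "describes changes in theta Cordance over time in both placebo and medication groups". The dated expectations are at week 1 and come from medication work.

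**The concern.** A primary hypothesis that names its metrics, window and population should have an analysis that names the same ones. Here the two differ on all three counts. A reader of the results could not tell whether a reported metric and visit were the ones the hypothesis called for, or the ones that looked best among those available.

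The window matters for interpretation as well as for error rates. Hypothesis 1 is about early prediction. Response is measured from beginning to endpoint, so a QEEG change at endpoint coincides with the outcome, and one at week 8 comes late in a 12-week treatment. An association there is not evidence of early prediction.

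The protocol describes the study as an underpowered pilot meant to supply effect sizes for larger studies. Picking the strongest of many small-sample contrasts would inflate exactly that output.

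**Working it through.** **Step 1. Hypothesis 1 set against the SAP**

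| Element | Hypothesis 1 | SAP | Status |
|---|---|---|---|
| ATR | named, as a change | calculated; no change score stated | partly covered |
| EEG Bispectrum | named | not mentioned | omitted |
| Cordance | named | background reference only | undetermined |
| Window | baseline to week 2 | all subsequent visits | week 2 included, not designated |
| Population | CBT patients | Pooled, Drug-only, Drug+CBT | no group labelled CBT-only |

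*Cordance.* Protocol I.C describes "Cordance, a QEEG measure integrating absolute and relative power of the signal". It is a derived index of power, so the undefined Power metrics may or may not include it.

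*ATR.* Protocol V(a) says that the index already contains percent change from baseline in relative theta power. A post-baseline ATR value therefore carries some change information, but the ATR change that Hypothesis 1 specifies is not listed among the derived variables.

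*Groups.* The protocol randomises 1:1 to CBT or escitalopram and has no combined arm. Drug+CBT could be a mislabelled CBT arm, both arms together (which would duplicate Pooled), or something else. The SAP does not say.

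**Step 2. Number of tests left open**

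The documents give no figure for this and state no alpha; 0.05 two-sided is assumed. Power is counted as a single metric, although the SAP uses the plural and names no band or site.

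Hypothesis 1 as stated: 3 metrics x 1 window x 1 arm = 3 tests. The chance of at least one false positive if independent is 1 - 0.95^3 = 0.143.

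The SAP under different readings:

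| Reading | Tests | 1 - 0.95^m |
|---|---|---|
| ATR and Power, 4 visits, one grouping | 2 x 4 x 1 = 8 | 0.337 |
| Power change only, 4 visits, 3 groupings | 1 x 4 x 3 = 12 | 0.460 |
| ATR and Power, 4 visits, 2 distinct groupings (Drug+CBT same as Pooled) | 2 x 4 x 2 = 16 | 0.560 |
| ATR and Power, 4 visits, 3 groupings | 2 x 4 x 3 = 24 | 0.708 |

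For two-sided tests on jointly normal statistics, independence gives the largest value. The last row therefore lies between 5% (perfectly correlated) and 71%. Correlation is certain here: visits repeat on the same patients, Pooled contains the Drug-only patients, and ATR contains relative theta power. The expected number of false positives under a global null, 24 x 0.05 = 1.2, does not depend on correlation.

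**Step 3. Sample for the CBT-only contrast**

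The protocol states power of 0.80 at 34, 0.76 at 30 and 0.47 at 15 per group, without an effect size or alpha. Assuming a two-sided 0.05 two-sample t test and solving from 34 per group gives d = 0.690, hence 0.747 at 30 and 0.446 at 15, close to the stated figures. With the same d, 15 CBT patients split 7 to 8 into responders and non-responders give power 0.235, and a 5 to 10 split gives 0.215. Dropout lowers these further, because the SAP analyses completers.

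**The case against.** Several stronger readings are tempting, and the documents do not support them.

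- *Two of the three metrics are dropped.* Only Bispectrum is shown to be absent. Cordance is built from absolute and relative power and may sit within the Power metrics.
- *Part of the primary hypothesis is never tested.* Protocol VI(a) plans a comparison of QEEG changes in CBT responders and non-responders, in wording broad enough to cover all three metrics. This stands as a limit on the claim. It does not cure the problem, because that section ties no metric or week to a test, and the SAP specifies a different test and leaves out the regression.
- *The week-2 window has been replaced by week 1.* Week 2 is a scheduled visit and falls within the subsequent visits. The week-1 expectation is background from drug studies. The fault is that no visit is designated.
- *Later recordings have no place in the analysis.* They serve Primary Aim 2 on biological changes under CBT, and Secondary Aim 1 on clinical functioning. They need only be kept apart from the Hypothesis 1 test.
- *The false-positive rate is 71%.* That is a ceiling, and it counts groupings outside Hypothesis 1. Within one grouping the corresponding ceiling is 34%.

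It is also fair to say that a declared pilot need not carry a confirmatory primary family. But a pilot intended to supply effect sizes still has to say which effects those are.

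**Conclusion.** The concern holds in a limited form. Of the three metrics in Hypothesis 1, one is named in the SAP without the stated change score (ATR), one is omitted (Bispectrum) and one is undetermined (cordance). The week-2 contrast is available but not designated, and no group labelled CBT-only is listed. This goes beyond missing detail: the analysis described differs from the hypothesis it should serve.

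Between 8 and 24 tests are left open, depending on the reading, against 3 for Hypothesis 1. The chance of at least one false positive is bounded above by 34% to 71%, assuming 0.05 per test, one Power metric and all four post-baseline visits; the true values are lower by an amount the documents do not allow one to compute. The SAP is dated 12/7/2017 and written in the past tense, so a reader might infer that metrics or visits were chosen after results were seen. The documents do not show that; they only fail to rule it out.

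**What to change.** 1. Define the Hypothesis 1 analysis as the baseline-to-week-2 change in ATR, Bispectrum and cordance, compared between responders and non-responders in the CBT arm. Report all three, with estimates and intervals, whatever the result.
2. Define the Power metrics and say whether they include cordance. If any of the three metrics could not be computed, say so and give the reason.
3. Label other Power metrics, other visits and other groupings as exploratory, or assign each to the aim it serves.
4. Reconcile Drug+CBT with the two randomised arms.
5. Disclose which choices of metric, visit and grouping were made after results were seen. Naming a primary analysis now cannot undo selection that has already happened, so this disclosure is needed alongside item 1.

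**Cost.** Mostly SAP wording, plus some reprocessing of recorded EEGs. Protocol V(a) says that recordings are analysed off-line, with metrics calculated by the device company. The documents do not show whether Bispectrum can still be obtained, which is why item 2 allows a documented omission. The CBT-only contrast also uses a smaller sample: about 15 patients before dropout, with power near 0.22 to 0.24 under the assumptions above. The results should therefore be presented as effect estimates with wide intervals.

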#### *E. Summary and Rationale:*

Studies which identify validated surrogate markers at baseline or soon after starting treatment that can predict response to treatment have the potential to refine the standard of care for depression, as these predictor studies will reduce the amount of time that clinicians spend adjusting treatments to find the most optimal treatment option. Additionally, studies which compare predictive biomarkers between treatments, particularly between psychotherapy and pharmacotherapy, will further enable clinicians to choose an optimal treatment.

To our knowledge, QEEG has not been studied in the prediction of response to CBT, an important and widely used non-pharmacologic approach to treating depression. Establishing QEEG technology as a predictor of response to CBT could help to guide treatment selection for individual patients. It is probable that certain patient populations are more likely to respond to either psychotherapeutic or psychopharmacological interventions, while others may benefit from a combination of treatment modalities. The public health significance of a valid technology that provides an objective means of determining likelihood of response to treatment would be enormous. This study will provide preliminary information about the utility of QEEG as a predictor of response in psychotherapy and will furnish the knowledge base of QEEG changes related to clinical variables, providing pilot data for a study in a larger sample.

Additionally, very few studies have assessed changes in reward responsiveness as a function of treatment. It is possible that CBT and pharmacological interventions have different effects on reward responsiveness and anhedonia, and thus the use of this task will allow us to investigate the influence of different treatments on reward processing in this population. We expect that the results of this study will guide future research with the ultimate goal of identifying a behavioral indicator of underlying dysfunction in reward related brain regions. Finally, it is possible that the reward responsiveness will act as a predictor of response to both psychotherapy and pharmacological treatment.

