#### **IV. Subject Enrollment**

*A. Methods of enrollment/registration/randomization:*

Patients are usually screened by telephone to determine tentative eligibility for studies. The subjects then are invited to come to MGH for a full psychiatric diagnostic interview. Patients accepted into the study will be registered through the Depression Clinical and Research Program. Randomization numbers will be provided by the study Biostatistician and will be maintained by the research pharmacists at MGH Research Pharmacy, who will administer the open label escitalopram, 10-20 mg/day, to those subjects who have been randomized to receive medication. The randomization will be 1:1, i.e. half of the patients will be randomized to receive escitalopram (10-20 mg/day, flexible dose) and half will be randomized to receive twelve weekly 50-minute

Cognitive Behavioral Therapy sessions. Both treatment interventions have been strongly validated by the literature, and are considered standard of care for this population.

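### The SAP's Drug+CBT group matches neither randomised arm, so no SAP group is, as labelled, the CBT-only set that Primary Aim 1 requires

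*SAP*

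**What the plan says.** The SAP's Methods section gives the analysis sets in one sentence: "The data were analyzed for 3 groups: Pooled, Drug-only, Drug+CBT". It defines none of them and does not say which one answers which aim. The SAP is written in the past tense and dated December 2017, so it reads as an account of analyses already done.

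The protocol describes two arms, each with one treatment:

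- Section IV.A: "The randomization will be 1:1, i.e. half of the patients will be randomized to receive escitalopram", with the other half allocated to weekly CBT.
- Section V(a): "eligible patients (n = 30) will be randomized to either CBT or to standard pharmacotherapy with an SSRI".
- Section II, Secondary Aim 1, names the arms: "in both arms (CBT vs. escitalopram".

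The first primary aim concerns CBT alone: "Primary Aim 1: To determine whether QEEG technology can predict whether a patient with MDD will respond to CBT". Section VI(a) plans a Mann-Whitney U test of QEEG change in CBT responders against CBT non-responders. Hypothesis 1 sets the window (start of treatment to two weeks) and the metrics (ATR, EEG Bispectrum, cordance).

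**The concern.** A reader who meets a result labelled Drug+CBT cannot tell whose data it describes. No arm received both treatments, and no SAP group is labelled as the CBT arm. On a literal reading, the comparison needed for Primary Aim 1 is missing from the SAP.

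The protocol presents the trial as a pilot whose purpose is to measure effect sizes for larger studies. An effect size from an unidentified set of patients cannot serve that purpose. Primary Aim 2 is affected as well, because it needs a CBT estimate to set beside the escitalopram estimate.

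**Working it through.** The point rests on comparing texts. The arithmetic only sizes it.

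**1. Planned arm size.** Section V(a) gives 30 patients and section IV.A gives 1:1 allocation, so 30 × 1/2 = 15 per arm. This agrees with the 15 per group in section VI(a). The power of 0.47 quoted there plays no part in this point.

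**2. SAP labels against the arms.**

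| SAP label | Possible meaning | Patients by plan |
|---|---|---|
| Pooled | both arms | 30 |
| Drug-only | escitalopram arm | 15 |
| Drug+CBT, reading (a) | patients given both treatments | 0 |
| Drug+CBT, reading (b) | both arms together, the same as Pooled | 30 |
| Drug+CBT, reading (c) | slip for the CBT arm | 15 |

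These counts are ceilings. The SAP analysed completers with available EEGs, and it gives no numbers.

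Reading (a) has no support in the design. Inclusion criterion 5 requires patients to be free of antidepressants for four weeks before screening. The protocol describes no step at which a CBT patient is given escitalopram, and the SAP's own title sets psychotherapy *versus* antidepressant treatment. The background does remark that some patients respond better to one modality "while others may benefit from a combination of treatment modalities", and section VIII(b) refers loosely to therapy and/or medications. Neither describes an arm. Reading (c) makes the three groups coherent, since Pooled is then the sum of the other two, but no sentence confirms it.

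**3. Aim 1 against the SAP groups.** Aim 1 needs responders and non-responders within the CBT arm. Explicitly CBT-only labels in the SAP: 0 of 3.

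**4. Whether Pooled could stand in.** Hypothesis 2 says: "QEEG parameters, different from those that predict response to pharmacotherapy, will be associated with response to CBT". If that is right, the two arms should not share one responder difference. As an illustration, assume equal arms and equal response rates. The pooled responder-minus-non-responder difference is then the average of the two arm differences. If the drug difference is *r* times the CBT difference, the pooled value is (1 + *r*)/2 of the CBT difference:

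| *r* | −1 | −0.5 | 0 | 0.5 | 1 |
|---|---|---|---|---|---|
| pooled share | 0% | 25% | 50% | 75% | 100% |

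The values of *r* are chosen, and values outside this range are possible, so the table is not a bound. It shows only that the pooled figure does not identify the CBT figure.

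**5. Precision of a CBT-only estimate.** Take the probability that a responder's change exceeds a non-responder's. Its standard error under no difference is √[(n₁ + n₂ + 1)/(12 n₁ n₂)]. For an assumed 7/8 split this is √[16/(12 × 56)] = 0.154, so the 95% half-width around 0.50 is 1.96 × 0.154 = 0.30. Other assumed splits of 15 give 0.32 (5/10), 0.34 (4/11) and 0.38 (3/12). Ten patients split 5/5 also give 0.38. This imprecision comes from the sample size, not from the label.

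**The case against.** The best reply is that this is an obvious typing slip. With Pooled and Drug-only already listed, the remaining group is naturally CBT, and a one-word correction closes the matter. Much of that stands: it is the likeliest reading, and the correction is cheap. But it remains an inference about who was analysed for a primary aim, and only the sponsor can confirm it.

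A second reply is that the protocol already defines the Aim 1 comparison. That is right. Section VI(a) is clear on which patients are compared, so the defect lies in the SAP, which does not carry that set over.

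Two stronger readings are tempting, and the documents do not support them:

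- A reader might infer that Pooled was offered as the answer to Aim 1. The SAP does not say so.
- A reader might take the SAP's contrast between theta changes in medication responders and placebo responders to mean that CBT would move opposite to drug. This trial has no placebo arm, and the SAP states no expectation for CBT. Hypothesis 2 alone is enough reason not to rely on pooling.

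**Conclusion.** The SAP's grouping is wrong as written. One of its three labels matches no randomised arm, and none is explicitly the CBT-only set. By plan, the same label could describe 0, about 30 or about 15 patients. That conclusion needs only the protocol's design and the SAP's sentence. The pooled shares and half-widths are illustrations under the assumptions stated with them.

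A reader might go further and infer that CBT patients went unanalysed or that Aim 1 was never tested. The documents do not show that. If the label is a slip, the comparison may well have been done on the right patients.

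The following discrepancies are separate, and correcting the label resolves none of them:

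- The SAP uses t tests where section VI(a) has Mann-Whitney U.
- The SAP uses completers, while section VI(b) defines an endpoint that takes in early-termination visits.
- The SAP counts a reduction of exactly 50% as response, while Hypothesis 1 has "Clinical response (defined as >50% change in HAMD-17 from beginning to endpoint").

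**What to change.** 1. Confirm from the analysis files which patients were in Drug+CBT.
2. Restate the SAP groups by randomised arm: CBT-only (Primary Aim 1), escitalopram-only, and pooled. Give the number analysed, responders and non-responders in each.
3. If the CBT-only comparison was not run, run it on existing data as the protocol sets it out. Use Mann-Whitney U (section VI(a)) on change from baseline to week 2 in the Hypothesis 1 metrics: ATR, EEG Bispectrum and cordance. The SAP mentions only ATR and power metrics, so say which of the three are available. State the response cut-off used, and label the result as added after the data were analysed.
4. Report an effect size with its confidence interval as a pilot estimate. Show the CBT and escitalopram estimates side by side for Primary Aim 2, and do not use the pooled result for Aim 1.

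The cost is a wording correction and a small table of counts. If step 3 is needed, add one two-group comparison for each available metric. No new data are required. The downside is that at most about 15 CBT patients are available by plan, so the estimate will be imprecise and cannot settle Aim 1.

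### The SAP's Pooled responder t test has no arm term, so it assumes one response effect common to escitalopram and CBT, which Hypothesis 2 gives reason to doubt

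*SAP*

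**What the plan says.** The protocol (IV. Subject Enrollment; V. Study Procedures) randomises 30 patients 1:1 to escitalopram or CBT. There is no placebo arm and no combination arm. Hypothesis 2 (II. Specific Aims) reads: "QEEG parameters, different from those that predict response to pharmacotherapy, will be associated with response to CBT". In VI. Statistical Analysis, the protocol's responder comparison is a Mann-Whitney test within the CBT arm.

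The SAP's Methods paragraph lists its analysis sets: "The data were analyzed for 3 groups: Pooled, Drug-only, Drug+CBT". It then says that "independent sample t tests were used to assess the relationship between responders" and change in QEEG metrics, among completers. It mentions no arm term, stratification or interaction.

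The SAP's Summary gives an expectation for medication: "decrease in theta activity from baseline at week 1 in responders, and an increase in non-responders". It adds that "Prior work showed an increase in theta activity in" placebo responders, with theta roughly flat in placebo non-responders. It gives directions but no magnitudes. For ATR it gives an expectation for medication responders only. It gives no expectation of any kind for CBT.

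**The concern.** A t test on the pooled patients estimates one responder-minus-non-responder difference. That difference has a clear meaning only if it is the same in both arms. Hypothesis 2 proposes that it is not, and the theta findings that the SAP cites show that the direction can depend on treatment. Three things can go wrong:

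- **Dilution.** An effect in one arm is averaged with none in the other.
- **Cancellation.** Effects of opposite sign offset each other.
- **Confounding by arm.** If the drug moves theta in everyone and one arm has more responders, the drug's effect on theta appears as a relation with response.

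The pooled test also answers neither primary aim. Aim 1 is about response to CBT, and Aim 2 is about how the treatments differ. The protocol presents the trial as a pilot meant to supply effect sizes for larger work, and an average of unlike effects would be a poor input.

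**Working it through.** **Inputs.** From the protocol: 15 per arm; power 0.80 at 34 per group, 0.76 at 30 and 0.47 at 15. Assumed, because the documents do not give them: two-sided alpha 0.05, SD 1, the response rates, all 15 per arm completing, and the size of any drug shift in theta.

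**The plan's own figure.** Solving for the effect size at 34 per group: d = (1.960 + 0.842) × √(2/34) = 0.68. Then:

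- at 30 per group, 0.68/√(2/30) − 1.960 gives power 0.75 (stated 0.76);
- at 15 per group, 0.68/√(2/15) − 1.960 gives 0.46 (stated 0.47).

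The stated figures reproduce to within about one point. Solving with the noncentral t gives d = 0.69, which is used below.

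**Pooled contrast at 50% response.** There are about 15 responders and 15 non-responders, so SE = √(1/15 + 1/15) = 0.365, and the t critical value on 28 df is 2.048. Power is approximated by P(Z > 2.048 − contrast/SE), adding the other tail where it matters.

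- *Same effect in both arms.* Contrast 0.69; 0.69/0.365 = 1.89; power about 0.44. Simulation: 0.43 to 0.44.
- *Effect in the drug arm only.* Contrast 0.69/2 = 0.345; 0.345/0.365 = 0.945; P(Z > 1.10) is about 0.135. Simulation: 0.13 to 0.14. A t test in the drug arm alone, with half the patients, has power of about 0.23.
- *Equal and opposite effects.* Contrast 0. Simulation: about 4% rejection.
- *CBT assumed to follow the placebo pattern, full-size rise.* Drug responders −0.345, drug non-responders +0.345, CBT responders +0.69, CBT non-responders 0. Responder mean (−0.345 + 0.69)/2 = 0.17; non-responder mean (0.345 + 0)/2 = 0.17; contrast 0; about 4% rejection.
- *The same with half that rise.* Responder mean 0, non-responder mean 0.17, contrast −0.17; 6% to 6.5% rejection.

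**Confounding by arm.** Suppose there is no response effect but the drug shifts theta by δ in everyone. The spurious contrast is δ times the difference between responders and non-responders in the share on drug.

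- At 40% v 60% response the shares are 0.40 and 0.60, a difference of 0.20. Simulated rejection with δ = 1 SD is about 5% with responder counts held fixed and 7% to 8% with response drawn at random per patient.
- At 40% v 70% the shares are 40/110 = 0.36 and 60/90 = 0.67, a difference of 0.30. Rejection is about 7% (fixed) to 12% (random).
- With equal response rates the spurious contrast is 0.
- With an arm term, rejection stays at about 5% throughout.

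**What an arm term can and cannot do.** It removes the confounding. It does not undo cancellation: with equal and opposite effects the arm-adjusted response test still rejects about 4%, while an arm-by-response interaction test rejects about 43%.

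**The case against.** The strongest reply has four parts.

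1. A reader might infer that the SAP expects theta to rise in CBT responders, so that cancellation is built into the plan. The documents do not support that. The rise is a prior finding in placebo responders, this trial has no placebo arm, and the SAP gives no direction for CBT. Hypothesis 2 says different parameters, not opposite changes in the same one. If a different metric carries the CBT signal, the result is dilution. This part stands, and cancellation is therefore stated only as conditional.
2. The SAP lists a Drug-only analysis, so the drug-arm result is not hidden. This stands. No set is labelled CBT-only, however, and Drug+CBT is undefined in a trial without a combination arm. It could mean both arms together, which would duplicate Pooled, or it could be a label for the CBT arm. One should not infer that the CBT arm was never analysed alone; the text does not settle it.
3. Confounding needs both a general drug effect on theta and unequal response rates. Neither is in the documents, and the inflation is modest unless the rates differ widely. This stands.
4. The trial is an acknowledged underpowered pilot, and neither document names the pooled result as primary. This too stands, and it would be speculation to call that result the headline. It does not remove the case for change, since effect sizes are the pilot's stated product.

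**Conclusion.** The concern holds in a limited form. The pooled t test assumes a common response effect that Hypothesis 2 calls into question. The consequence that needs least assumption is dilution: power of about 0.13 to 0.14 if a 0.69 SD effect exists in the drug arm only, against 0.43 to 0.44 if both arms share it. Near-complete loss (about 4% to 6.5% rejection) requires CBT responders to behave like placebo responders. False-positive inflation is modest under an assumed 1-SD drug shift: about 5% to 8% at 40% v 60% response and 7% to 12% at 40% v 70%.

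The documents do not show that any of this happened, only that the pooled test could not reveal it. The directional argument concerns theta; for ATR, only Hypothesis 2 bears on the matter. All figures assume 15 completers per arm. The SAP analyses completers and does not give their number, so actual power may be lower.

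**What to change.** In the SAP, replace the unstratified pooled t test with:

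- the responder-minus-non-responder difference and its confidence interval within each randomised arm (escitalopram alone, CBT alone);
- an arm-by-response interaction estimate with its confidence interval;
- any combined figure only from a model with arm as a term, always shown beside the two by-arm estimates.

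The combined figure should not depend on the two estimates having the same sign. With a true common effect of 0.69 SD the signs would disagree in about 17% to 18% of trials of this size. With no effect, a figure shown only when the signs agree would be nominally significant about 10% of the time. The SAP should also define Pooled and Drug+CBT in terms of the randomised arms.

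The cost is revised wording and a re-run on existing data: one degree of freedom for arm, a second for the interaction, and about 0.01 of power for the combined estimate. The interaction will be imprecise. With about 7.5 patients per cell its SE is √(4/7.5) = 0.73 SD, a 95% interval of about ±2.056 × 0.73 = ±1.5 SD (26 df). It should be reported as an estimate, and a non-significant result should not be read as evidence that the arms agree.
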